6.1.9 DURATION OF THERAPY

The duration of therapy is 12 weeks.

6.1.10 TRACKING OF DOSE

XR-NTX or XR-PLC is dispensed by the local site pharmacy and administered by a health care professional in the research clinic. The local site pharmacy keeps record of the electronic order for dispensing the medication and the research clinic provider tracks the administration at time of injection in a research note.

SL-BUP or SL-PLC is dispensed by the local site pharmacy. The local site pharmacy keeps record of the electronic order for dispensing the medication and the clinical research assistant tracks the pill count at the return visits. The participant is instructed to bring any unused medication back to the research clinic at each visit.

6.1.11 DEVICE SPECIFIC CONSIDERATIONS

Not applicable.

6.2 STUDY AGENT ACCOUNTABILITY PROCEDURES

Each local site Pharmacy is responsible for study medication receipt, storage, dispensing, accounting for inventory, and destruction of unused medication. Each local site Pharmacy has standard operational procedures for the handling of research medications and controlled medications that are required to be adhered to for this study.

7 STUDY PROCEDURES AND SCHEDULE

7.1 STUDY PROCEDURES/EVALUATIONS

7.1.1 STUDY SPECIFIC PROCEDURES

Rater Training and CAPS-5 Fidelity Monitoring: An independent rater at each site performs the Timeline Follow Back (TLFB), Clinician Administered PTSD Scale for DSM-5 (CAPS-5), and Columbia Suicide Severity Rating (C-SSR) assessments. The independent rater is kept masked to the treatment assignment and does not assess adverse events (to avoid accidental unmasking) and remains therapeutically neutral (to avoid an inflated placebo response). In consultation with [name]., all independent raters undergo training and certification by [name] and [name] prior to assessing study participants. CAPS-5 inter-rater reliability coefficients in the range of 0.90 to 0.95 will be established and repeated annually. The audio-recordings of TLFB and CAPS-5 assessments are sent to the Tuscaloosa research team via a secure data transmission method (shared VA server access) and Tuscaloosa research team sends the recordings on an encrypted disc to [name] via chain of custody mail. [name] or a trained designee listens to at least 25% of the recordings for consensus scoring and give personalized written feedback to the independent raters. If there is rater-drift, the rater receives additional training from [name], [name], and/or [name]. To the extent possible, participants are evaluated by the same independent rater throughout their duration in the study. Back-up raters are trained and certified.

Table below provides a brief description of the study instruments that will be utilized during the course of this study.

Description of Study Instruments	
SCREENING or BASELINE (Administered by trained investigator or CRC)	

MINI International Neuropsychiatric Interview for DSM-5 (MINI-5)²¹ is an updated semi-structured clinician-administered interview for DSM-5 diagnoses. To reduce participant burden, modules B (Suicidality), L (anorexia nervosa), M (bulimia), N (generalized anxiety), P (antisocial) and optional assessment measures will not be collected. Purpose: To document current and past psychiatric diagnoses and confirm eligibility criteria for AUD, PTSD and excluded diagnoses; administered by trained local site investigator (LSI), assessor, or CRC.
	

Clinical Institute Withdrawal Assessment of Alcohol Scale, Revised (CIWA-Ar)²² is an interviewer-driven measure of alcohol withdrawal used to identify withdrawal symptoms requiring medical treatment.
	

Alcohol Dependence Scale (ADS)²³ is a self-report measure of alcohol dependence that is used as a measure for group differences in severity of alcohol dependence at baseline.
	

Clinical Opiate Withdrawal Scale (COWS)²⁴ is an 11-item clinician-administered scale used to rate common signs and symptoms of opiate withdrawal, to make sure participants meet baseline eligibility.
	

Ohio State University Traumatic Brain Injury Identification Method – Short Form (OSU-TBI)^{25,26} is an interviewer-administered questionnaire of history and severity of TBI to characterize sample and determine eligibility.
	

Barratt Impulsivity Scale (BIS)²⁷ is a 30-item self-report instrument that uses a 4-point scale for declarative “I” statements meant to be answered quickly that is used to assess the behavioral construct of impulsiveness.
	

Life Events Checklist for DSM-5 (LEC-5)^{28,29} is a self-report that assesses exposure to 16 traumatic events, as a preface to the CAPS-5, to provide an anchor of the index trauma and document category of trauma.
	
SCREENING, BASELINE, AND FOLLOW-UP (Administered by certified independent assessor)	

Timeline Follow Back (TLFB)³⁰ is a calendar-based method of assessing drinking patterns used to document the frequency and amount of daily alcohol consumption and to categorize the World Health Organization Risk Levels of Alcohol Use.
	

Clinician-Administered PTSD Scale for DSM-5 (CAPS-5)³¹ is a 30-item structured interview to assess PTSD severity for baseline eligibility (total score $\leq 26$³²) and outcome of treatment.
	

Columbia-Suicide Severity Rating Scale (C-SSRS)³³ is clinician-administered interview to measure suicidality and document suicidal behavior used to evaluate recent suicidality, ideation, and suicidal behavior for eligibility at baseline (past two months) and to track emergent suicidality at Week 8.
	
BASELINE AND FOLLOW-UP INSTRUMENTS	

PTSD Checklist for DSM-5 (PCL-5)^{34,35} is a 20-item self-report measure that assesses the DSM-5 symptoms of PTSD and is used in confirmatory analysis of change in PTSD symptoms.
	

Short Inventory of Problems (SIP)³⁶ measures adverse consequences of alcohol abuse in five areas: Interpersonal, Physical, Social, Impulsive, and Intrapersonal total adverse consequences.
	

Obsessive Compulsive Drinking Scale (OCDS)³⁷ measures obsessive and compulsive thoughts related to drinking alcohol and is used as a measure craving for alcohol.
	

Desire of Alcohol Questionnaire (DAQ)³⁸ is a self-report measure that assesses (a) desires/intentions to drink, (b) negative reinforcement, and (c) positive reinforcement and ability to control drinking. DAQ scores have been found to increase during cue exposure and after alcohol administration in the laboratory and is used to measure desire/intentions, negative and positive reinforcements for alcohol during the stress reactivity paradigm.
	

Clinical Global Impression-Severity & Clinical Global Impression-Improvement (CGI-S/CGI-I)³⁹ are two single-item 7-point clinician-rated scales used to measure global change in severity of illness and status of improvement.
	

Patient Health Questionnaire (PHQ-9)⁴⁰ is a validated 9-item self-report measure of depressive symptoms used to measure change in depression and has one item that is used to monitor suicidality (safety measure).
	

Veterans RAND 12-Item Health Survey (VR-12)⁴¹ is used to assess functioning domains: physical functioning, role limitations due to physical problems, bodily pain, general health perceptions, energy/vitality, social functioning, role limitations due to emotional problems, and mental health.
	

Adverse Events (AE) are assessed by a research team member at each assessment using Food and Drug Administration (FDA) standards for AE reporting. AEs, SAE are reported to the DSMB, and local IRB.
	

Psychophysiological Studies*: Local site research personnel are trained by [name].

*Psychophysiologic assessments are optional to not be a barrier to enrollment or randomization.

Fear Conditioning and Extinction Paradigm (Assessment Time: Preparation 15 min, Acquisition phase 20 min, and Extinction phase: 20 min.) The participant undergoes the two-day psychophysiological assessments, prior to beginning the study medication.

Fear Acquisition: The following method has been used successfully in [name] previous studies to generate a robust fear response. The unconditioned stimulus (US) is a 250-millisecond blast of air with an intensity of 140 psi directed to the larynx. The conditioned stimuli (CS's) are different colored shapes presented on a computer monitor in front of the participant. The startle probe is presented after six seconds and is followed by the US 500 milliseconds seconds later. The CS+ is paired with the air blast, while the CS- is not. The acquisition session consists of a habituation phase and a conditioning phase with three blocks of four trials of each type (noise alone, (NA), CS+, CS-) in each block.

Fear-potentiated startle is defined as the increase in the magnitude of the acoustic startle response in the presence of a cue that has been paired with an aversive US. Startle responses to a CS stimulus are compared to startle responses to the noise alone. Fear-potentiated startle is calculated by subtracting the startle magnitude to the noise probe alone (termed noise alone or NA trials) from startle in the presence of the CS stimuli and expressed as a difference score. For this reason, trial types are termed NA, CS+ (paired to airblast US), and CS- (not paired to an airblast US). Successful fear conditioning is observed by an increase in startle to the CS+ (paired with an airblast US) as compared to noise alone and a significant difference to the CS+ as compared to the CS- (this is termed CS discrimination).

Fear Extinction: The following method allows us to assess fear extinction and has been used successfully in our previous studies.⁴⁹ The extinction session occurs ten minutes after acquisition. Neither the CS+ nor the CS- are paired with the US. The extinction session consists of six blocks of four trials of each type (NA, CS+ (unreinforced), and CS-) in each block.

Extinction Recall: The test of spontaneous recovery of fear occurs 24 hours after fear conditioning and consists of one block of four trials of each type (NA, CS+ (unreinforced), and CS-). This paradigm has been used successfully in healthy volunteers as well as combat Veterans seeking treatment in the Trauma Recovery Program. After completing this test, three unpaired air blasts are delivered during a subsequent session to measure reinstatement effects.

Psychophysiological Reactivity to Trauma-Evoking and Alcohol-Related Stimuli using Virtual Reality (VR) Exposure: (Assessment time: Trauma related reactivity: 8 min and Alcohol cues reactivity: 8 min.)

Participants view a computer-generated VR environment that includes combat-related contexts associated with deployment (e.g., Middle Eastern city, combat scenes, barracks, military vehicles). A second paradigm using computer-generated VR environment for alcohol-related stimuli is subsequently conducted. If the participant is someone who experienced sexual trauma as the cause of his/her PTSD, he/she will view a high definition video that contains

images or sounds associated with assault in locations such as barracks, latrines, rear seat of a vehicle instead of combat scenes. These contexts do not recreate the assault. A third paradigm for non-combat, non-sexual trauma will be used for civilian participants with non-sexual trauma.

Acoustic Startle Assessment: As described in our prior work, the eye-blink component of the acoustic startle response is measured by electromyography (EMG) recordings of the right orbicularis oculi muscle with two 5-mm Ag/AgCl electrodes filled with electrolyte gel. This is done by scrubbing on the cheek below the eye with a special cleanser and attaching two electrodes to the skin just below the eye. The startle probe is a 108-dB (A) SPL, 40 ms burst of broadband noise with near instantaneous rise time, delivered binaurally through headphones (Model TDH 39, Maico, Inc.). The startle response data is acquired using Biopac MP150 for Windows (Biopac Systems, Inc.). All data are sampled at 1000 Hz and amplified with a gain of 5000 using the EMG module of the Biopac system. The acquired data are filtered, rectified, and smoothed using MindWare software (MindWare Technologies, Ltd.) and exported for statistical analyses. The maximum amplitude of muscle contraction 20–200 ms after the startle probe is used as a measure of the startle response.

Galvanic Skin Response (GSR, Skin Conductance Level): We measure skin conductance reactivity based upon the amount of perspiration on the skin. Two 5-mm Ag/AgCl disposable electrodes filled with isotonic paste are attached to middle phalanges of the second and fourth finger of the non-dominant hand. We assess tonic skin conductance and skin conductance change from baseline during the above-mentioned psychophysiological tasks. The skin conductance level and skin resistance data are acquired at a sampling rate of 1 kHz using the GSR module of the Biopac system. Additionally, skin conductance level (SCL) and skin conductance response (SCR) data are acquired at a sampling rate of 10 Hz using the eSense system connected to a secure, study designated iPad. Two 5 mm Ag/AgCl electrodes filled with isotonic paste are attached to middle phalanges of the second and fourth finger of the non-dominant hand during the Stress Reactivity to Trauma Evoking Stimuli portion of the study. The acquired data are exported for further analyses.

Heart Rate (HR) and Respiration: Heart rate is measured throughout the psychophysiological assessment by attaching two Ag/AgCl electrodes, one below the right clavicle and the other on the left forearm. High frequency heart-rate variability is quantified from spectral analysis of HR in the 0.12 to 0.40 Hz frequency band. Heart rate is recorded at a sampling rate of 1 kHz using the ECG module of the Biopac system. The dependent variables are HR, respiratory sinus arrhythmia (RSA), and HR reactivity as previously performed by members of our research group. Respiration (breathing rate) is measured throughout the psychophysiological assessment by attaching an elastic band around the participant's chest.

7.1.2 STANDARD OF CARE STUDY PROCEDURES

No procedures or assessments for this study are considered standard of care.

7.1.3 MEDICAL MANAGEMENT

At each visit, the participant meets with the medication provider (MD, PharmD, RN, or APN)

who is qualified to provide Medical Management⁴² (MM). MM includes instructions on the study medication, adjust the dosing, and evaluate side effects. The initial visit focuses on educating the patient on medication regimen and adherence, negative consequences of drinking, and other health issues. Follow-up visits focus on medication adherence, evaluating and managing side effects, and psychoeducation. The MM provider remains masked to the treatment assignment and is not involved in the outcome assessments. The CRC is responsible for the pill count and gives the pill count information to the MM provider for use in counseling the participant on the importance of adherence to the treatment and dosing. Adverse events might be identified during MM and subsequently documented and reported according to instructions in Section 8.

7.2 LABORATORY PROCEDURES/EVALUATIONS

7.2.1 CLINICAL LABORATORY EVALUATIONS

Laboratory studies (complete blood count, comprehensive chemistry which includes liver and kidney function tests) are performed at screening and end of treatment (Week 12) or early termination visit. *Additional labs may need to be drawn at Week 4 and Week 8 depending on ALT and AST values at screening and study enrollment.

- Laboratory tests (except for pregnancy tests and urine drug screens) performed within 90 days of screening are acceptable for study screening purposes.
- All laboratory test results are reviewed by the investigator or qualified designee and acknowledged.
- Any value outside of the normal range is flagged and the investigator determines whether it is clinically significant.
- If a test is questionable, the test(s) may be repeated, or additional testing done to provide clarification.
- Unscheduled laboratory testing may be done at the discretion of the investigator for appropriate medical care.

- **Hematology** – White blood cell count (WBC), Red blood cell count (RBC), hemoglobin (Hgb), hematocrit (Hct), mean corpuscular volume (MCV), platelet count (PLT)
- **Thyroid Function** – Thyroid Stimulating Hormone (TSH) at screening only to confirm participant eligibility.
- **Serum Chemistry** – basic metabolic panel (BMP); must include liver (ALT, AST, GGT) and kidney function labs (BUN and Creatinine). However, GGT is collected at baseline, Week 8 and Week 12.

Added procedures with v7:

- If baseline ALT or AST is between 3x to 5x ULN
 - Recheck ALT and AST at Week 4 visit:
 - If ALT or AST >4x ULN, PI may consider discontinuing the study medication if clinically indicated.
 - Recheck ALT and AST at Week 8 visit:

- If ALT or AST >3x ULN , PI may consider discontinuing the study medication if clinically indicated.
- The PI may consult with the medical monitor as needed.

A history and physical (H&P) and ECG within the prior 90-days is acceptable for the study screening purposes; otherwise, it should be repeated.

Pregnancy Testing: Urine pregnancy dip tests for women of childbearing potential are processed in the research clinic by a member of the study team at screening, Week 4, Week 8, and Week 12 (or end of study/early study termination), as well as any time that pregnancy is suspected.

Urine Drug Screening: Urine samples are collected using a CLIA waived 10 panel drug test. Urine drug screens are conducted in the research clinic by a member of the study team at screening, baseline, and each study visit. The results are retained in the participant's research files. Urine drug screen results are not entered into the participant's medical record.

Buprenorphine is not included in the urine drug screen to avoid accidental un-masking of the study team members to the treatment arm. Osmolality, temperature, pH, and adulterants will be assessed at collection time to ensure sample validity.

Alcohol Breathalyzer Test: Breathalyzer tests are conducted at each research visit in the research clinic by a trained clinical research coordinator and used to measure participants' breathalyzed alcohol concentration (BrAC). Samples >0.01 g/dl are considered positive. Results are kept in research records and not entered in medical records.

(Note: this test may not be conducted if restricted by local COVID protocols).

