2.3 POTENTIAL RISKS AND BENEFITS

2.3.1 POTENTIAL RISKS

Naltrexone for extended-release injectable suspension (XR-NTX; Vivitrol) is FDA-indicated for the treatment of alcohol dependence, so participants in this study may have direct benefit from this treatment. XR-NTX is not a controlled substance.

Sublingual buprenorphine (SL-BUP) is FDA-indicated for the treatment of opioid dependence. SL-BUP is a Schedule III narcotic under the Controlled Substances Act. The use of SL-BUP in a non-opioid dependent population has a risk of misuse or abuse. Buprenorphine is a partial agonist at the mu-opioid receptor and chronic administration produces physical dependence of the opioid type, characterized by withdrawal signs and symptoms upon abrupt discontinuation or rapid taper. The withdrawal syndrome is typically milder than seen with full agonists and may be delayed in onset. However, to mitigate the potential for misuse, dependency, and withdrawal, buprenorphine can be combined with XR-NTX, a medication that blocks the mu receptor involved in psychogenic properties of buprenorphine.

XR-NTX can antagonize the effects of opioids via competitive inhibition of opioid receptors, which raises the concern that the combination of SL-BUP and XR-NTX will make SL-BUP less effective. This would be a risk for individuals who are using opiates or SL-BUP on a regular basis prior to starting XR-NTX, (i.e., the addition of XR-NTX may precipitate opioid withdrawal symptoms). For this reason, this study excludes patients who have recent opioid use or opioid use disorders, and opiates are not allowed to be concurrently taken during the study. XR-NTX is contraindicated in patients receiving opioid analgesics and in patients with current physiologic opioid dependence, acute opiate withdrawal, acute hepatitis or liver failure, and previous hypersensitivity reaction to XR-NTX. Patients with these contraindications are not eligible to participate in this study.

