5.2 PARTICIPANT EXCLUSION CRITERIA

To be enrolled in this study, participants must not meet the following criteria.

1. Current diagnosis of DSM-5 bipolar I, schizophrenia, schizoaffective, and/or major depressive disorder with psychotic features (defined by MINI-5 at screening).
2. Increased risk of suicide that necessitates inpatient treatment or warrants therapy excluded by the protocol, and/or current suicidal plan, per investigator clinical judgement, based on interview and defined on the Columbia Suicidality Severity Rating Scale (C-SSRS).
3. Treatment with trauma-focused therapy for PTSD (e.g., Cognitive Processing Therapy, Prolonged Exposure, or EMDR) within two weeks of baseline study visit. Note: Supportive psychotherapy in process for PTSD at time of Screening may be continued.
4. Current diagnosis of severe non-alcohol substance use disorder (except for caffeine and nicotine) during the preceding 1 month, based on participant screening interview.
5. Use of opioids within 2 weeks of baseline or opioid use disorder in the previous 90 days.
6. History of severe traumatic brain injury (TBI) per Ohio State University TBI Identification Method. Note: history of mild or moderate TBI is allowed.
7. Any clinically significant, uncontrolled, or medical/surgical condition that would contraindicate use of SL-BUP + XR-NTX, or limit ability to complete study assessments, including seizure disorders (other than childhood febrile seizures), severe renal insufficiency, significant arrhythmia or heart block, heart failure, or myocardial infarction within the past 2 years, severe thrombocytopenia or hemophilia, severe hepatic failure, complete hearing loss, and/or need for surgery that might interfere with ability to participate.
8. Clinically significant laboratory abnormalities, including a thyroid stimulating hormone (TSH) >1.5 times upper limit of normal, hyperthyroidism, cardiovascular findings QTcF ≥ 500 msec on electrocardiogram (ECG) or blood pressure $>190/110$, and aspartate aminotransferase and/or alanine aminotransferase > 5 times upper limit of normal.
9. History of allergic reaction, bronchospasm or hypersensitivity to a naltrexone or buprenorphine.

10. Unable or unwilling to refrain from medications thought to influence alcohol consumption (see inclusion criteria above.)

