them as a study participant, and eliciting commitment. The investigators also provide ongoing reinforcement of the patients' commitment to long-term follow-up and medication adherence. The study medication and visits are provided at no cost. The study medication providers emphasize the need to properly adhere to prescribed treatments or to call to revise the treatments if side effects occur or therapeutic effects are lost.

The participant receives a modest payment for each attended visit to offset the inconvenience of the follow-up appointments and transportation costs. The site IRBs have approved similar payments in the past and have not viewed the amount as coercive. Service members cannot be paid while on active duty but may be reimbursed for travel costs. Participants are paid more on the days of the psychophysiological testing since these visits require more time. Participants exiting early are encouraged to undergo Week 12 assessments and are paid Week 12 amount.

After consenting to participate, a urine drug screen and breathalyzer will be conducted at each visit. If the drug screen is positive for opiates at screening or baseline visit and/or if the participant has a breathalyzer level > 0.02 at any visit, the appointment will be canceled and rescheduled, and the participant will not be paid for the canceled appointment. The CRC may reschedule the appointment for a later date. If the urine drug screen is positive for opiates at follow-up visits, the investigator must assess the safety of continuing the participant on study medication, but the visit does not need to be canceled.

Schedule of Participation Payments																
	Screening, Baseline, Week (#) or Telephone (T) Visit															
	Screen	Base-line	1	2	T	4	T	6	T	8	T	10	T	12	T	14
Outcome Visits	25	75	25	25		75		25		75		25		50		25
Psychophysiology testing		50 2d								50 2d						

The above payment schedule offers maximum for study participation of \$425 for medication outcomes without psychophysiological assessments and \$525 with psychophysiological assessments. (Note: There is flexibility for sites to adjust their participation payment amounts, for instance West Haven has a minimum payment amount of \$25)

Also, sites can pay for transportation or provide a \$25 gas/gift card to offset transportation costs if needed, at the discretion of investigator and TREAC Executive Director.

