*Smoking: Will include both tobacco and marijuana at baseline, and marijuana only at Weeks 8 and 12. **H&P, laboratory tests, and ECG within previous 90 days is acceptable at screening visit. (At Week 12: The H&P, thyroid test, and ECG do not need to be repeated.) If baseline level was between 3x-5x ULN, ALT and AST needs to be repeated at week 4 and week 8 visit. At Week 8, GGT needs to be repeated. ^aVital signs and breathalyzer on Week 2, 6, 10 may be omitted due to COVID-19 reduction of in-person visits. ^bPsychophysiological assessments are optional so as to not be a barrier to enrollment or randomization. ***Day of Randomization is on Baseline. The schedule of follow-up visits is anchored to Baseline. ****CAPS-5 and C-SSRS can be administered prior to day of baseline so long as it is within one week of day of randomization and scores are entered as baseline. ****C-SSRS can be done either at screening or baseline visit, as well as Week 8. ^{\$}Baseline and week 8 drug dispensing will occur on day 1 if not participating in psychophysiology testing and on day 2 if participating in testing

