7.3.3 BASELINE AND RANDOMIZATION VISITS

The investigators and CRCs provide ongoing support and education during the study to reinforce the participants' commitment and resolve logistical barriers to keeping the appointments. Participant burden is kept to a minimum (i.e., small number of assessments and low frequency). Adherence and attendance are vital to the success of both treatment and the study. Patient education on study procedures and the treatment approach in the study is the cornerstone to promote adherence. To maximize participant retention, study coordinators are trained to have a substantial focus, especially in the first several meetings with participants, on developing a strong alliance, educating them about the study, understanding the importance of adhering to treatment, what is expected of them as a study participant, and eliciting commitment.

At the baseline visit, the research team evaluates the participant per the study instruments listed in the Schedule of Assessments table in 7.3.1. Participants undergoing the optional two-day psychophysiological assessments, as described above, will complete both days of the psychophysiological testing prior to beginning the study medication.

The research medication provider enters the medication orders (one for XR-NTX and one for SL-BUP) and the local site pharmacy dispenses the study medication according to the randomized assignment to one of two treatments:

- **Treatment A (SL-BUP 2mg + XR-NTX 380mg) or**
- **Treatment B (SL-PLC and XR-PLC).**

SL-BUP is taken daily and XR-NTX is given every 4 weeks. All medications are dispensed by local site pharmacies with clearly labeled instructions.

The participant receives the first dose of XR-NTX injectable in the research clinic and remains in the clinic under the supervision of the research team for approximately 1 hour after the 1st dose is administered.

The medication provider or trained CRC reviews the medication instructions with the participant (how to administer sublingual, keeping up with medication dosing, and need to return any

unused medication to the research medication provider at the next visit). The participant initiates SL-BUP on the following day.

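### The urine screen leaves out buprenorphine at screening and baseline for a masking reason that cannot apply there, so no assay for it is planned before the first naltrexone depot

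*Protocol*

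**What the plan says.** **The test.** Protocol section 7.2.1 (Urine Drug Screening) uses one 10-panel cup throughout: "Urine drug screens are conducted in the research clinic by a member of the study team at screening, baseline, and each study visit". The next paragraph adds: "Buprenorphine is not included in the urine drug screen to avoid accidental un-masking of the study team members to the treatment arm". The sentence makes no distinction between visits before and after dosing.

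**The risk.** Section 2.3.1 says that XR-NTX may precipitate opioid withdrawal, and describes who is exposed: "This would be a risk for individuals who are using opiates or SL-BUP on a regular basis prior to starting XR-NTX". It then gives the mitigation: "For this reason, this study excludes patients who have recent opioid use or opioid use disorders". Section 8.7 repeats both statements.

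**The exclusion.** Criterion 5 in section 5.2, repeated in SAP section 4.2.1, reads: "Use of opioids within 2 weeks of baseline or opioid use disorder in the previous 90 days". It names no method of verification.

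**The action on a positive result.** Section 5.3 cancels and reschedules the visit under this condition: "If the drug screen is positive for opiates at screening or baseline visit".

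**The sequence.** The notes to the schedule in section 7.3.1 state: "Day of Randomization is on Baseline". Section 7.3.3 has the first injection given in the clinic and then says: "The participant initiates SL-BUP on the following day".

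**The concern.** The protocol names a hazard, relies on an exclusion to control it, and then removes from its drug screen the analyte that would help enforce that exclusion for buprenorphine. The reason offered, protecting the mask, is sound once study drug has been taken. It appears to have been carried over to two visits where it has no work to do.

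What is at stake is mainly participant safety. Someone with regular, undisclosed buprenorphine use who is randomised to active treatment receives a naltrexone injection designed to act for four weeks. Section 6.1.7 requires no oral naltrexone beforehand, and sections 2.3.1 and 8.7 describe the drug as leaving the body gradually. An error at entry is therefore not quickly undone.

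**Working it through.** The check concerns sequence and coverage, so no power or error-rate arithmetic applies.

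**Step 1. Can a pre-dose positive reveal the arm?**

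| Event | Source in Protocol | Arm assigned? | Study buprenorphine taken? |
|---|---|---|---|
| Screening urine | 7.2.1, 7.3.1 | No | No |
| Baseline urine | 7.2.1, 7.3.1 | Not if taken before randomisation | No |
| Randomisation, on the baseline day | 7.3.1 notes | Yes | No |
| First XR-NTX or placebo injection | 7.3.3 | Yes | No |
| First SL-BUP or placebo tablet, the following day | 7.3.3 | Yes | Yes, if active |

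At both pre-dose urine collections the last column reads No. A buprenorphine-positive result there can only reflect non-study drug, so it carries no information about the arm. Sections 5.3 and 7.3.2 describe the baseline visit as separate from the day of randomisation, whereas the notes to 7.3.1 place randomisation on Baseline. The conclusion is the same on either reading. It would hold even if the baseline urine were collected after the injection, because the tablets start a day later. Section 5.3 cancels a baseline visit on an opiate positive, which implies that the result is meant to be known before treatment.

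**Step 2. Is buprenorphine measured anywhere else before the first injection?**

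- Urine: 2 scheduled collections (screening, baseline), with buprenorphine omitted at both. Count: 0 of 2.
- Serum: Weeks 8 and 12 only, for adherence (Protocol 7.3.1 and 10.4.5; SAP 4.5, 8.3 and 9.6.1). Count before the first injection: 0.
- Total planned buprenorphine assays before the first injection: 0 + 0 = 0.

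**Step 3. What do the other pre-randomisation checks cover?**

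| Check | Source in Protocol | What it can and cannot show |
|---|---|---|
| Diagnostic and screening interview | 5.2, 7.1.1 | Depends on disclosure |
| Concomitant medications, with 60 days of prior psychotropics | 7.3.1, 7.6 | Depends on disclosure or a recorded prescription |
| Prohibited list, which names a buprenorphine product | 7.5 | A rule, not a means of detection |
| COWS at screening | 7.1.1, 7.3.1 | Rates withdrawal signs; a current user not in withdrawal can score low |
| Unscheduled laboratory tests | 7.2.1 | Discretionary; needs prior suspicion |

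None of these is an assay. Each can miss regular use that is undisclosed and unprescribed in someone who is not in withdrawal. Criterion 5 bars opioid use disorder only within the previous 90 days, so people with an older history can be eligible.

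**The case against.** **Several checks already stand before randomisation.** This is correct. Section 7.3.3 also keeps participants under supervision for about an hour after the first injection, although that responds to an event and does not prevent it. A reader might infer that prior buprenorphine use goes wholly unchecked. The documents do not support that; what is missing is a planned biochemical test. The group left exposed is narrow: regular users with no disclosure, no recorded prescription and no withdrawal signs.

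**One kit at all visits is a defensible safeguard.** A single cup without buprenorphine makes it impossible to use the wrong cup after dosing. The protocol does not give this as its reason, but it is a real cost of the change. It can be handled by a site instruction, and it does not make the stated reason apply before dosing.

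**Buprenorphine may not be the only gap.** A reader might infer that it is the one opioid the protocol names, or the only one untested. Neither follows. Section 2.3.1 refers to opiates as well as SL-BUP, section 7.5 lists many opioids, and the ten analytes are not given. The text establishes only that buprenorphine is left out.

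**The serum samples would show contamination anyway.** A reader might infer that the omission also undermines the serum adherence measure. The documents do not bear this out. Placebo participants receive no study buprenorphine, so any found in their serum at Week 8 or 12 is already identifiable as non-study drug. In the active arm, a negative baseline urine would not settle the source eight weeks later, because outside use can begin after randomisation. The point therefore rests on safety at entry alone.

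**Conclusion.** The point holds. Masking is the only reason given for omitting buprenorphine, and it cannot operate at screening or at baseline before dosing. As a result, a risk named twice in the protocol is controlled before the first 380 mg depot by history, observation and discretion, with zero planned assays.

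The documents give no prevalence of undisclosed buprenorphine use in this population, so the number of participants affected cannot be estimated, and no case is made from an assumed count. Partial safeguards exist and the exposed group is likely to be small. The change is worth making because the hazard is the protocol's own and urine is already collected at both visits.

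The conclusion rests on two readings of the text: that the omission sentence applies to every visit, since it states no exception, and that SL-BUP is never taken before the day after the first injection. It does not depend on sample size, power or any assumed rate. It does not question the omission after dosing, which is sound.

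**What to change.** **In section 7.2.1**, limit the omission to visits after the first dose. Possible wording: *The urine drug screen includes buprenorphine at screening and at baseline before randomisation. It is omitted from all later screens to protect masking, and the kit containing buprenorphine is not to be used once study drug has been given.*

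**Across sections 2.3.1, 5.2, 5.3, 7.2.1 and 8.7**, reconcile the text so that a pre-randomisation buprenorphine positive is handled under exclusion 5 as it now stands. Section 5.3 currently provides for cancelling and rescheduling after an opiate positive, while exclusion 5 has a two-week window. The sponsor should state how the two fit together and whether the term opiates in 5.3 covers buprenorphine. No change to the exclusion itself is proposed here.

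**Cost.** A short protocol edit, a buprenorphine strip or a different cup at two visits where urine is already taken, and two kit types to stock. The downside is a small risk of unmasking if a site uses the wrong kit after dosing, which the site instruction addresses. The test would not detect outside use that begins after baseline.
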